Appendix

Abbreviations

| AE | Adverse Event |
|-------|---|
| HIPAA | Health Insurance Portability and Accountability Act |
| IRB | Institutional Review Board |
| PI | Principal Investigator |
| PHI | Personal Health Information |
| RCT | Randomized Controlled Trial |
| SAE | Serious Adverse Event |
| US | United States |
| IUD | Intrauterine Device |
| EMB | Endometrial Biopsy |
| FDA | Food and Drug Administration |

1.0 Background & Rationale

When intrauterine procedures are performed, often the cervix needs to be stabilized to facilitate intrauterine entry. The standard approach for cervical stabilization is an invasive, sharp instrument called a tenaculum. This leaves two punctures on the cervix, which can be painful and bleed, which can prolong any intrauterine procedure (IUD insertion, endometrial biopsy, etc). Aspivix [™] has created a **suction-based atraumatic cervical stabilizer** for use with such intrauterine procedures. The First-in-Woman study (RCT with 100 patients) completed in 2 renowned University Hospitals in Switzerland showed positive results (pain reduced by up to 73% and bleeding occurrence reduced by 78%). This new device is **fully FDA approved**.

I've attached the company's data and the clinical brochure showing the device, explaining how it is used, and data on effectiveness. In addition, this is their RCT publication on the journal *Contraception* on this device, showing the data cited above (Attachment #1).

https://www.contraceptionjournal.org/article/S0010-7824(23)00066-5/fulltext

Aspivix [™] launched the AMBASSADOR PROGRAM, a 3–6-month program with free of charge devices for selected hospitals /clinics willing to test extensively Carevix[™] in multiple transcervical procedures.

2.0 Objective(s)

2.1 Primary Objective

2.1.1 Primary Objective: to assess patient-reported pain and provider-reported bleeding. Our hypothesis is that patient-reported pain and provider-reported bleeding comparing Carevix[™] to tenaculum will be similar in our American population and with all intrauterine procedures as it was in the European study and with only IUD insertions.

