2.2 Secondary Objective

2.2.1 Secondary Objective: to assess provider-reported ease of use and provider satisfaction.

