3.0 Outcome Measures/Endpoints

3.1 Primary Outcome Measures

3.1.1 Primary outcome measures: To assess patient-reported pain, a questionnaire provided by Aspivix [™] (Attachment #2) will be done after completing the procedure. This takes, on average, 1 minute to complete.

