3.2 Secondary Outcome Measures

3.2.1 Secondary outcome measures: To assess provider-reported bleeding, ease of use and provider satisfaction with the device, the provider will complete a questionnaire following the patient's completion of their portion of the questionnaire (Attachment #2). This takes, on average, 2 minutes to complete.

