12.0 Statistical Considerations

We performed sample size/power calculations with the primary outcome of pain (visual analog scale) at the time of Carevix[™]/tenaculum use. Thirty participants per group (total N=60) are needed to achieve at least 80% power and a two-sided 5% significance level. Descriptive characteristics of those in the Carevix[™] and control groups will be compared using standard statistical testing such as Chi-square and t-tests. Differences in outcomes between the device and control groups will similarly utilize standard testing.

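### Bleeding is part of the primary objective (2.1.1) but a secondary outcome (3.2.1) with no power statement, and no planned analysis addresses an effect 'similar' in size to the European study's

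*Combined protocol and SAP*

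**What the plan says.** **Objectives.** Section 2.1.1 states the primary objective as "to assess patient-reported pain and provider-reported bleeding" and includes both in its hypothesis. Section 2.2.1 gives the secondary objective as "to assess provider-reported ease of use and provider satisfaction"; bleeding is not there.

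**Outcomes.** Section 3.1.1 reads "Primary outcome measures: To assess patient-reported pain" and names no other primary outcome. Section 3.2.1 reads "To assess provider-reported bleeding, ease of use and provider satisfaction with the device", so bleeding is secondary.

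**Sample size and analysis.** Section 12.0 says "We performed sample size/power calculations with the primary outcome of pain (visual analog scale" and continues "Thirty participants per group (total N=60) are needed to achieve at least 80% power", at a two-sided 5% level. It gives no pain difference, no SD and no statement about bleeding. The outcome analysis is one sentence: "Differences in outcomes between the device and control groups will similarly utilize standard testing".

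**Comparison with the European study.** Section 2.1.1 hypothesises that the Carevix-versus-tenaculum comparison will be similar to the European one, in an American population and across all intrauterine procedures. Section 5.0 repeats this as the purpose of the study. Section 1.0 cites the European results as pain reduced by up to 73% and bleeding by 78%. No section defines similar.

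**The concern.** Bleeding serves only the primary objective, yet it is ranked as a secondary outcome. Suppose pain shows no significant difference and bleeding does. Under 2.1.1 the investigators could say that part of the primary objective was met; under 3.1.1, 3.2.1 and 12.0 they could not. The plan has no rule to decide, so the choice could be made after the data are seen.

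If bleeding is meant to be primary, half of the primary objective has no stated power. The similarity aim raises a different issue: testing whether two devices differ in this cohort is not the same as asking whether the size of that difference agrees with an earlier study's estimate.

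**Working it through.** **1. The plan's own figure.** Section 12.0 gives 30 per group, power of at least 80% and two-sided 5%, but neither a difference nor an SD, so the 30 cannot be reproduced. It can only be inverted:

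d = (1.960 + 0.842) × √(2/30) = 2.802 × 0.258 = 0.72 SD (normal approximation), or 0.74 SD from a t-test solver.

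The documents state neither value, so the figure is neither confirmed nor refuted, even for pain.

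**2. Endpoint status, side by side.**

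| Section | Pain | Bleeding |
|---|---|---|
| 2.1.1 primary objective and hypothesis | included | included |
| 2.2.1 secondary objective | – | absent |
| 3.1.1 primary outcome | included | absent |
| 3.2.1 secondary outcome | – | included |
| 12.0 sample size | called the primary outcome | absent |

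Three sections (3.1.1, 3.2.1, 12.0) agree on pain as primary and bleeding as not. The two objective sections do not fit them. If a significant result on either endpoint could meet the objective, each tested at 5%, the chance of at least one false positive would be 1 − 0.95² = 9.75% for independent tests.

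**3. Power for bleeding at 30 per group.** Inputs: n = 30 per group (12.0); 78% reduction (1.0), so the Carevix rate is p₂ = 0.22 × p₁; tenaculum rate p₁ assumed; bleeding item assumed to be yes/no.

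Power = Σₐ Σ_b Bin(a; 30, p₁) × Bin(b; 30, p₂), summed over all pairs of counts (31 × 31) with two-sided p ≤ 0.05.

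| Assumed p₁ | p₂ | Uncorrected chi-square | Fisher's exact |
|---|---|---|---|
| 20% | 4.4% | 50% | 27% |
| 30% | 6.6% | 69% | 54% |
| 40% | 8.8% | 84% | 76% |
| 50% | 11.0% | 93% | 89% |

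Power reaches 80% at a tenaculum rate of about 38% (chi-square) or 43% (Fisher).

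**4. What a difference test says about similarity in size.** Take 9/30 bleeding with tenaculum and 2/30 with Carevix as an illustration. The uncorrected chi-square is 60 × (9×28 − 2×21)² / (30 × 30 × 11 × 49) = 5.45, above 3.84, so the difference is significant. The risk ratio is 2/9 = 0.22, close to the European 78% reduction. The standard error of its log is √(1/2 − 1/30 + 1/9 − 1/30) = 0.738, and exp(1.96 × 0.738) = 4.25. The 95% CI is therefore 0.22/4.25 to 0.22 × 4.25, or 0.05 to 0.94. A significant result with the European point estimate is thus compatible with reductions from about 6% to 95%. With 15/30 versus 3/30 the interval is 0.06 to 0.62 around 0.20. For pain, the 95% CI half-width is t(0.975, 58) × √(2/30) = 2.00 × 0.258 = 0.52 SD.

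**The case against.** **Similar may mean only that the benefit is seen again.** This is an ordinary reading of 2.1.1. Under it, testing Carevix against tenaculum is the right analysis and only loose wording remains. This stands, so the point about the analysis is conditional on the other reading, similarity in size. A reader might infer that the planned test cannot serve the study's aim at all, or that an equivalence test with a margin is needed. The documents do not support either: they make no equivalence claim and set no margin.

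**If bleeding is secondary, it needs no power statement.** Correct. The power table matters only while 2.1.1 keeps bleeding in the primary objective. A reader might infer from it that 60 participants are too few for bleeding. That does not follow: power is ample at some plausible rates and poor at others, and the documents give no tenaculum rate. The 50% adverse-event level in 10.0 does not supply one, because it is a threshold for discussion that covers bleeding or injury.

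**The measure and time of the pain assessment are in 12.0.** One might see a conflict between pain at device use (12.0) and a questionnaire that "will be done after completing the procedure" (3.1.1). There is none: a later questionnaire can ask about pain at device use, and Attachment #2, not among the pages reviewed, may specify it.

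**Bleeding could legitimately be co-primary.** Also true, but the plan would have to say so in 3.1.1 and 12.0.

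**Conclusion.** The concern holds. The conflict over the status of bleeding is plain on the text and rests on no assumption: 2.1.1 and 2.2.1 cannot be reconciled with 3.1.1, 3.2.1 and 12.0. Power for bleeding is not established. Given the 78% reduction and a yes/no item, it runs from 27% or 50% (Fisher or chi-square) at an assumed 20% tenaculum rate to 89% or 93% at 50%. That shows how far the answer depends on an unstated rate; it does not show that the trial is too small. Nor should 12.0 be read as having demonstrated adequate power for pain, since it asserts 30 per group without inputs.

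The similarity part is less certain. If an effect of similar size is meant, the planned tests do not address it. If only a repeated advantage over the tenaculum is meant, 2.1.1 and 5.0 should say so. The matter should be corrected, but it does not call the conduct of the study into question.

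**What to change.** - **2.1.1:** state one primary hypothesis, that VAS pain at the time of device use differs between Carevix and tenaculum (two-sided 5%, as in 12.0).
- **2.2.1:** add bleeding, consistent with 3.2.1, and state that a bleeding result alone does not meet the primary objective.
- **2.1.1, 5.0 and 12.0:** replace the similarity claim with a descriptive presentation: pain and bleeding differences with 95% CIs beside the European estimates from Attachment #1, noting that the European study covered IUD insertions only while this one takes all intrauterine procedures.

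Alternative: if the investigators prefer bleeding as co-primary, 3.1.1 and 12.0 must say so, with a success rule (either endpoint with the alpha shared, or both required) and a power statement based on a stated tenaculum rate. An equal alpha split would lower pain power at 0.72 SD from 80% to 71%.

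Cost of the main option: wording in four sections, and reading the European estimates from Attachment #1. Sample size and data collection do not change. The price is a more modest claim on bleeding and on replication of the European result.

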5.0 Study Design

Aspivix, the company that created Carevix[™], launched the Ambassador Program, a 3-6 month program with free of charge devices for clinics willing to test Carevix[™] in multiple intrauterine procedures. Our clinic, Coleman Center, will conduct a prospective cohort study for 3-6 months where patients who qualify via inclusion criteria who are also receiving an intrauterine procedure (endometrial biopsy, IUD insertion, manual aspiration, etc) on the exposure (Carevix[™]) arm will have the opportunity to receive the Carevix[™] device for cervical stabilization, per provider preference (i.e., providers may decline to use Carevix[™] for endometrial biopsy).

Once 25 participants have received Carevix[™], recruitment for the control (tenaculum) arm will begin. Participants will receive the standard of care device if cervical stabilization is required. Each participant will be provided with a study information sheet and sign a consent form. They will then undergo their planned procedure, using the assigned device.

Following completion of their procedure, they will also agree to fill out a survey about their experience, which takes about 1 minute to complete. The provider performing the procedure will finish the survey with provider-specific questions about bleeding, ease of use and satisfaction. The purpose of this study is to compare Carevix[™] to the tenaculum and determine if the Carevix[™] shows similar results in the United States population as it has in the European study and with all intrauterine procedures.

*Once 25 of 30 patients received CarevixTM, will commence control group collection N = 30

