6.0 Enrollment

We intend to enroll twenty-five evaluable Carevix subjects prior to commencing the enrollment of the control-group tenaculum subjects. An additional five Carevix subjects (for a total of N=30) will be concurrently enrolled while accruing the thirty additional tenaculum subjects for a total enrollment of N=60.

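### The hypothesis is similarity to the European IUD-only trial, but Section 12 plans only device-versus-control difference tests, with no European comparison and no adjustment for procedure type

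*Combined protocol and SAP*

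**What the plan says.** **Hypothesis and purpose.** Section 2.1.1 expects patient-reported pain and provider-reported bleeding, Carevix versus tenaculum, to be such that they "will be similar in our American population and with all intrauterine procedures as it was in the European study", a study of IUD insertions only. Section 5 gives the purpose in two parts: to compare the devices, and to determine whether Carevix "shows similar results in the United States population as it has in the European study and with all intrauterine procedures".

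**Analysis.** Section 12 sizes the study "with the primary outcome of pain (visual analog scale) at the time of" device use, at 30 per group, two-sided 5% and at least 80% power. Baseline characteristics are compared by chi-square and t-tests. For outcomes it says: "Differences in outcomes between the device and control groups will similarly utilize standard testing". It gives no definition or margin for similarity, no comparison with the European estimates, and no analysis by or adjusted for procedure type. No other section supplies these.

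**How patients reach a device.** Section 5 offers Carevix "per provider preference (i.e., providers may decline to use Carevix" for endometrial biopsy). Section 7 adds that when the patient or the provider opts out of Carevix, the patient is asked to join with the tenaculum. Section 6 sets the order: "We intend to enroll twenty-five evaluable Carevix subjects prior to commencing the enrollment of the control-group tenaculum subjects".

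**Bleeding.** It is part of the primary objective in 2.1.1. Section 3.1.1 lists pain alone as primary, and 3.2.1 puts bleeding among the secondary outcomes: "To assess provider-reported bleeding, ease of use and provider satisfaction with the device, the provider will complete a questionnaire".

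**The concern.** A test against zero difference answers a different question from the one in 2.1.1. A significant result would leave open whether the US effect is close to the European one. A non-significant result would not show that it is unlike the European one. With no rule for what similar means, either result could be written up as confirming or refuting the hypothesis after the data are seen.

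Procedure type also matters within the US comparison. If biopsies go mainly to the tenaculum arm and pain differs between procedures, the unadjusted device difference carries part of the procedure difference. The same imbalance would blur any comparison of a pooled US result with an IUD-only trial.

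**Working it through.** **Inputs from the documents.** 30 per group, two-sided 5%, at least 80% power (Section 12). The European trial had 100 patients, with pain reduced by up to 73% and bleeding by 78% (Section 1.0). No SD, absolute means, bleeding rates, margin or procedure split is given, so results are in SD units of pain. Nothing comparable can be computed for bleeding.

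**1. The plan's own figure.** N cannot be reproduced forward without an effect size, but it can be solved backward. Detectable difference = (1.960 + 0.842) × √(2/30) = 0.72 SD (0.74 SD by t-test). So 30 per group is consistent with an ordinary difference test.

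**2. What that test can say about size.** Half-width = t(.975, 58) × √(1/30 + 1/30) = 0.517 SD. An observed difference of 0.74 SD would have an interval of 0.74 ± 0.52, that is 0.22 to 1.26 SD: clear on direction, wide on size.

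**3. US effect minus European effect.** Assume 50 per arm in the European trial and the same SD. Standard error = √(2/30 + 2/50) = 0.327; half-width = 1.96 × 0.327 = 0.64 SD.

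**4. Could similarity be tested at this N?** Two one-sided 5% tests, true effects equal, normal approximation: power = 2Φ(margin/SE − 1.645) − 1, set to zero if negative. The margins are assumptions.

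| Margin (SD) | European effect treated as exact (SE 0.258) | European effect with its own error (SE 0.327) |
|---|---|---|
| 0.5 | 23% | 0% |
| 0.75 | 79% | 49% |
| 1.0 | 97% | 84% |

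The right-hand column is the relevant one, because the reference is itself an estimate from 100 patients.

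**5. Procedure mix.** One assumed mix is used throughout: IUD insertions 24 of 30 with Carevix and 15 of 30 with tenaculum.
- Shift in the unadjusted device difference, if mean pain differs between procedures by 0.5 to 1.0 SD (assumption): (24/30 − 15/30) × 0.5 = 0.15 SD, up to 0.30 × 1.0 = 0.30 SD, in either direction.
- Half-width adjusted for procedure type: information = 24×15/39 + 6×15/21 = 13.52; t(.975, 57) × √(1/13.52) = 0.545 SD, against 0.517 unadjusted.
- IUD insertions only: t(.975, 37) × √(1/24 + 1/15) = 0.67 SD.
- Other procedures only: t(.975, 19) × √(1/6 + 1/15) = 1.01 SD.
- Difference in device effect, IUD versus other: t(.975, 56) × √(1/24 + 1/15 + 1/6 + 1/15) = 1.17 SD.

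**The case against.** The wording of 2.1.1 is loose. Similar may mean only that the benefit points the same way, and a difference test serves that reading. The purpose sentence in Section 5 begins with comparing the two devices, which is what Section 12 tests. On this view one undefined word needs defining, and little else. What stands is that the documents do not define the word, and that even on the mildest reading no analysis places the US result beside the European one.

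A reader might infer that the protocol promises a consistent effect in every type of procedure. The text does not require this. It can equally mean a pooled, mixed-procedure result compared with an IUD-only one, so the absence of a formal test of consistency is not an error. At this size such a test would tell little anyway (half-width 1.17 SD under the assumed mix).

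Section 12 does compare characteristics between groups, which would expose an imbalance in procedure type if that is among them. This is a real safeguard, but it detects imbalance without correcting for it. Pain is also defined at the time of device use, so it may depend less on the procedure that follows. The shift of 0.15 to 0.30 SD is therefore an illustration, not an estimate.

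The non-random, largely sequential design is openly disclosed. That is fair; what is missing is a statement of the limit it puts on each comparison.

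**Conclusion.** The mismatch stands on the text alone: the stated hypothesis concerns similarity to an external result, and the planned tests concern a difference between two US groups. They can support a difference and its direction, with a half-width of about 0.52 SD at 30 per arm, but not a similar size. The missing adjustment also stands, because Sections 5 and 7 let procedure type influence which device is used.

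Three stronger inferences are not supported:
- That N = 60 is wrong. It fits a difference of about 0.72 to 0.74 SD, and no stated figure is contradicted.
- That the device comparison will be biased. The documents give no procedure split and no pain difference between procedures.
- That procedure type is not recorded. The questionnaire (Attachment #2) is not shown, so this needs confirming only.

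The figures for 30 per arm rest on the documents. Every mix, margin and European arm-size figure is an assumption. This is worth correcting before analysis; it does not invalidate the study. The conflict over bleeding is real but separate.

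**What to change.** 1. **Sections 2.1.1 and 5.** State the tested hypothesis as a two-sided 5% difference in patient-reported pain between Carevix and tenaculum, and label the comparison with the European trial descriptive. If the team wants to keep similarity as a tested claim, it should state a margin that allows for the sampling error of both studies and check that N supports it.
2. **Section 12.** Report the device difference in pain with a 95% confidence interval, both unadjusted and adjusted for procedure type (IUD insertion versus other). Give the IUD-only estimate beside the European estimate on a common metric, since Section 1.0 quotes only relative reductions. State that no similarity claim will be drawn from a p-value.
3. **Limits of the design.** State that device use depends on patient choice, provider choice and enrolment phase, with 25 of 30 Carevix patients planned before control recruitment begins, and that this limits both the US comparison and the European one. Clarify when patients who opt out of Carevix under Section 7 may enter the tenaculum arm.
4. **Data.** Confirm that procedure type is captured for both arms, in the company survey and in REDCap. If the company survey lacks it, record it in REDCap, where Section 13 already plans to link surveys to consent by date and time.
5. **Separately,** reconcile bleeding as part of the primary objective (2.1.1) with its listing as a secondary outcome (3.2.1).

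**Cost.** No extra patients and at most one data field. Under the assumed 24/30 versus 15/30 mix, adjustment widens the half-width from 0.52 to about 0.55 SD, and the IUD-only estimate is imprecise at about 0.67 SD. The team gives up similarity to Europe as a confirmed finding unless it sets and supports a margin.

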2.2 Secondary Objective

2.2.1 Secondary Objective: to assess provider-reported ease of use and provider satisfaction.

3.0 Outcome Measures/Endpoints

3.1 Primary Outcome Measures

3.1.1 Primary outcome measures: To assess patient-reported pain, a questionnaire provided by Aspivix [™] (Attachment #2) will be done after completing the procedure. This takes, on average, 1 minute to complete.

3.2 Secondary Outcome Measures

3.2.1 Secondary outcome measures: To assess provider-reported bleeding, ease of use and provider satisfaction with the device, the provider will complete a questionnaire following the patient's completion of their portion of the questionnaire (Attachment #2). This takes, on average, 2 minutes to complete.

